#### 7.6 Withdrawal criteria

Participants will be allowed to withdraw from the study at any point. We will not collect any further data from this participant however will use data available during their time in the study for the final study analysis. If it is in the participant's best interest the clinician in charge of the study (AH) may also choose to withdraw the participant in the interests of their own health.

# 8 Regulatory and Ethical Considerations

#### 8.1 Study conduct

- The study will be conducted in accordance with the UK Policy Framework for Health and Social Care Research and other applicable guidance.
- The study will not commence until all regulatory approvals are in place, which will include HRA Approval, REC Approval and confirmation from local R&I that the Trust has capacity and capability to carry out the research.

#### 8.2 Monitoring and audit

- The study will be subject to the standard procedures for monitoring and auditing of studies by the sponsor.
- Any changes to the protocol will be agreed with the sponsor prior to submission to NHS research ethics committee for review with the exception of where urgent safety measures apply.
- All staff working in the study will have completed appropriate training to undertake the duties delegated to them by the Principal investigator such an ICH-GCP.

#### 8.3 **Protocol deviations**

- Any deviations to the protocol will be reported to the sponsor within 24 hours of the occurrence to allow an impact assessment to be completed.
- Consideration will be given to the nature of the deviation, its causes and the potential impact on the study.
- Where necessary, a deviation from the protocol may lead to an amendment to the protocol

#### 8.4 Study progress reports

The PI and research team will submit progress reports to the Sponsor as requested and prior to submission to NHS REC, in accordance with the terms and condition of the study approval.

#### 8.5 Stopping rules

It is not anticipated that the study will be stopped prior to its intended end-date. However, the study will be halted if:

- New information comes to light which means that the aims of the study are futile.
- Safety issues come to light regarding the intervention.
- Resources to conduct the study are no longer available.

## 9 Record keeping and data management

As the sponsor, Northern Care Alliance NHS Foundation Trust will be responsible for secure data storage on an encrypted Northern Care Alliance NHS Foundation Trust computer. The use of participant ID numbers on study documentation will allow analysis of pseudonymised data by our statistician at The University of Manchester who will remain blind to the randomisation group that participants were assigned to.

The electronic database will be kept at Northern Care Alliance NHS Foundation Trust and will be completely anonymised, password protected and only accessible to members of the study team.

# 10 Statistical analyses and data handling

#### Analysis

This is a feasibility study, so we will not be carrying out formal hypothesis testing to determine if the intervention is effective. Data analysis will follow an Intention-To-Treat (ITT) protocol and will be used to inform power calculations for a definitive trial in addition to other published sources. Attrition and reasons for drop-out will be recorded where possible. We will assess rates of missing data (and which elements in particular) and proportions of dropouts at different trial stages. We will also assess whether any of the measures display floor and/ or ceiling effects.

We will calculate and present in a CONSORT (Eldridge et al, 2010) flow chart: the proportion of people with CFQ scores greater than or equal to 4, consenting to the study; those entering the randomised phase; the proportion completing 50% and 100% intervention (using patient reported compliance sheet); the proportion completing follow-up assessments at 3 and 6 months post-randomisation.

We will summarise, as appropriate (e.g. mean/ standard deviation; median/ inter-quartile range; proportion/ 95% confidence interval; data range) data for all potential outcome measures, overall and by group. Outcome data and changes (mean differences) in patient-reported measures between baseline (initial clinical assessment) and 3 and 6 month follow-up will be plotted with 95% confidence intervals by randomisation group on an intention to treat basis.

Adherence with the intervention will be measured and used to calculate an estimate of dose response. Where participants adhere to all 3 stages of the intervention fully – using the intervention as intended daily this will be deemed full intervention, with non-use of any stages of the intervention as a zero dose.

The SD of the (potential) Primary Outcome, along with the estimated attrition rate and the average number recruited per PCT/CCG (plus the range of this data) will be used to help inform the sample size calculation for the large-scale RCT.

The Primary feasibility outcomes will be recruitment and retention rates, and we will gain an estimate of likely effect sizes of the self-help intervention for a range of outcome measures and based on this determine the appropriate sample size for a larger trial to evaluate its effectiveness and cost-effectiveness versus standard treatments delivered within an NHS CFS/ME Service.

Adverse events, including serious adverse reactions (SARS) to trial interventions will be reported to the Sponsor and recorded and reported within the CONSORT diagram.

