#### Phase 1: Survey to determine prevalence of 'Long COVID' in primary care

Patients will be recruited from general practice and provided a link to complete an online survey to determine levels of fatigue (physical and mental) using the Chalder fatigue Questionnaire – CFQ), physical functioning using SF-12 and quality of life using EQ5D at least 12 weeks after previously testing positive (SARS CoV-2) for COVID-19.

The results of CFQ will be used to screen respondents for 'Long COVID' with those scoring >= 4 on CFQ scored bimodally, being invited to participate in Phase 2 RCT. This will be advised on screen explaining that the symptoms they reported mean they are suitable to join the second phase of the study. A tick box on screen will allow those interested in participating to view a copy of the Participation Information Sheet (PIS) and Consent Form (CF) on screen and also receive a copy by email or post. Interested participants will be asked to provide their telephone number so the research practitioner can call them back to answer any questions they might have about the study and to take informed consent over the telephone for those who agree to participate. The data collected in the Phase 1 Survey will be used as the proxy baseline data for Phase 2 to reduce the need for participant to repeat measures unnecessarily.

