#### Phase 2: Wait-list RCT Intervention Study

Those eligible will receive a PIS and CF explaining the Phase 2 RCT study either by email or by post. After 5 days, participants will be telephoned by a research practitioner based in Northern Care Alliance NHS Foundation Trust's Research delivery team.

100 participants providing informed consent will be allocated 1:1 into a two-arm wait-list randomised control trial (RCT) comparing lymphatic self-massage technique (the intervention) plus any usual care (UC) from their healthcare professionals vs. UC alone. This means any treatment received by participants will not be constrained. Those in the intervention group will receive instructions and equipment required via post as soon as they are randomised, with the UC wait-list group receiving their equipment 3 months later (after completion of their 3m follow-up), meaning all Phase 2 participants will be given access to the intervention. Both groups will be asked to complete follow-up measures at 3m and 6m.

Qualitative interviews will be conducted with 10 participants in the intervention arm at 3 months and a further 10 in each of the intervention arm and UC arms at 6 months to assess acceptability of the intervention, adherence to the intervention (over time for intervention group) and to explore potential barriers and drivers to its use.

#### **Detailed Plan of Investigation** 7

Research Activity		Done	Year and Month										Responsible		
			1 2 3 4 5 6 7 8 9 10 11 12 13 14 15								15				
		-	*	4	2 4	-	0	1	0 3	10	11 12	13		13	
re-work: On run up to	research becoming active											L			
PPIE	Consultation and patient input	1	L									L			LR/RP
FARSITE	Agree FARSITE search criteria with NW e-Health/CRN	-	L									L			LR/AH/CRN
	Run FARSITE search - Indicative numbers		L									L			CRN
Qualtrics Survey	Set up Phase 1 survey	-	L									L			SB/LR/AH/RP/MH
	Set up & test Phase 2 eligibility checks	-	L									L			SB/LR/AH
	Set up Phase 2 surveys at 3m and 6m		L									L			SB/LR/AH
Approvals	Sponsorship		L									L			AH/LR
	Ethical application (IRAS)		L									L			AH/LR
hase 1: Online Survey	Capacity & Capability checks: Salford & GM		H	-	-	-	-	-	_		_	-	-	-	AH/LR
Engagement with GP			4	-	_	-		-	-			-	-		SB LR / RA (CRN)
Survey launch	Eligible patients receive invite from their GP		5						-			-	-		SB
Survey launch	Implied consent by completing survey - 0m data		- 2					-		+		-	-		GP Staff (CRN)

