Prior to FARSITE data being available, we had used recruitment trajectories based on a 'Recruitment Estimate' of 28,720 potentially eligible participants in Greater Manchester, equating to 2.9% with positive SARS-CoV-2 test recorded in their GP notes (FARSITE Data provided by Greater Manchester Comprehensive Research Network using data at April 2021). Applying this same rate to Salford's 226,000 adult population we anticipate identification of approximately 6,554 COVID-19 positive patients, although June data now suggest 14,083 eligible adults within Salford GP practices alone.

We anticipate that around 50% of those eligible to take part in the Phase 1 study will be willing to take part in the study, this number is based on 51% households in England participating in ONS Coronavirus Infection Survey (https://www.ons.gov.uk/peoplepopulationandcommunity/healthandsocialcare/conditionsanddi seases/bulletins/coronaviruscovid19infectionsurveypilot/previousReleases) although we expect uptake to an invitation via the patients GP may be higher.

\*Sponsor's representative: [name], Managing Director of Research & Innovation Norther Care Alliance NHS Foundation Trust, [name] [contact]; email: [contact]

Whilst work on infection rates has been the focus, there is much less work around the prevalence of Long COVID and individual symptoms, so we do not have confirmed percentages of those likely to meet CFQ cut-off scores. Data modelling by Northern Care Alliance NHS Foundation Trust surveillance unit however adopts a 'Long COVID' rate of 10% having symptoms at 4 weeks or longer, with fatigue being the major symptom (https://www.ons.gov.uk/peoplepopulationandcommunity/healthandsocialcare/healthandlifeex pectancies/datasets/prevalenceoflongcovidsymptomsandcovid19complications).

Assuming an uptake rate of 50% into the Phase 2 Intervention for those who meet the screening criteria based on CFQ agreeing to participate in the Phase 2 intervention, we should be able to recruit our proposed sample size of 100 by 4 months. This is based on invitation letters being sent out to 4000 patients, 2000 of whom we hope will participate in the survey, 200 of which may have Long COVID fatigue related symptoms, with 100 agreeing to participate in the intervention study.

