#### Randomisation for Phase 2 Intervention RCT

Randomisation will be carried out using an internal STATA routine (Chaimani et al. 2013) by an independent member of the University of Manchester Biostatistics Group who will be responsible for this, along with conveying the allocation to the RA in order for the intervention pack to be sent to participants. This method ensures the statistician carrying out the analyses (MH) remains masked to treatment allocation.

Eligible participants will be allocated at random (1:1) in blocks of size 4, 6 or 8 (chosen at random and in equal numbers) to either the immediate lymphatic self-massage intervention plus UC or UC alone plus the intervention from 3 months. Due to the known gender differences between women and men both in terms of CFS/ME and also Long COVID itself, we will stratify for gender within the randomisation. We will set up the randomisation so that should extra sites outside of Salford be required to achieve recruitment targets, we will ensure a balance between the two trial arms.

All Phase 2 participants will receive a letter thanking them for completing the Phase 1 survey and letting them know which group they have been allocated to. The letter will explain how RCTs work and the importance of follow-up data irrespective of which group participants are allocated to, and that all participants will receive the intervention described but at different times, and that they will be followed up for 6 months in total (at 3m and 6m) using the same survey measures they have already completed in the baseline survey. One additional tick sheet will be used to capture participants' use of the intervention which will be sent to the intervention participants at 3m and 6m and to the control – wait-list group at 6 m only.

The group randomised to receive the intervention will receive this immediately after randomisation along with this letter. The UC wait-list control group will be sent the intervention pack after submission of their 3m follow-up data. We will not tell patients when to stop using the intervention but will monitor its use in the two study arms over time.

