#### Follow-ups

Survey data collected in Phase 1 will be treated as baseline or 0-month data. Table 1 shows the schedule for subsequent study assessments. The CFQ, SF-12 and EQ5D-5D will be completed by the patient online or via a paper form returned to the research office. The 3m follow-up allows us to see any changes between those receiving the intervention and those not. The 6-month (6m) follow-up enables us to see if any benefits observed at 3m are maintained beyond the intervention period, and to compare this between the two groups.

	0m (baseline)	3m	6m
CFQ	Х	Х	Х
SF-12	Х	Х	Х
EQ-5D-5L	Х	Х	Х
Intervention diary		X (intervention group only)	X
Qualitative interview		X	X

Table 1: Assessments and timescales for the feasibility study

Proposed Primary outcome measures: These will be the logistical findings arising from the feasibility study (i.e. related to the conduct of the trial)

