#### Secondary 'Clinical' Outcome measures;

**Chalder Fatigue Questionnaire (CFQ) (Chalder et al., 1993)**: Our data analysis of CFQ scores at 3m will compare those who have used the intervention (on an intention to treat ITT basis – i.e. assuming those randomised to receive the intervention use it as intended) vs those who have not.

**SF-12** (https://www.rand.org/health-care/surveys\_tools/mos/12-item-short-form.html): This self-reported outcome measure developed from the Medical Outcomes Study assesses the impact of health on an individual's everyday life. It is often used as a quality-of-life measure and will be used to see if differences exist in quality of life between the two groups.

**Euroquol EQ-5D-5L (htpps://euroquol.org)**: This will permit us to calculate change in quality of life and determine Quality Adjusted Life Years scores (QALYs) for the intervention and waitlist control comparison group over 9m.

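### The planned confidence intervals describe each arm's outcome and its change from the score that selected participants; the 3-month between-arm difference, as allocated, should be named as the effect estimate.

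*Protocol*

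**What the plan says.** **Baseline.** The protocol's Phase 1 design text invites respondents at or above the CFQ cut-off into Phase 2, and then states: "The data collected in the Phase 1 Survey will be used as the proxy baseline data for Phase 2". The Follow-ups text in section 7.1 repeats this: "Survey data collected in Phase 1 will be treated as baseline or 0-month data".

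**Display.** Section 10 sets out plots of outcome values and of change over time. Its wording for the change plots is: "measures between baseline (initial clinical assessment) and 3 and 6 month follow-up will be plotted with 95% confidence intervals by randomisation group". The analysis is to be by intention to treat. The mean differences mentioned in that sentence are differences over time, not between arms. The preceding sentence in section 10 offers summaries overall and by group. Neither sentence gives an interval for the difference between arms.

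**Between-arm comparison.** One is planned. Section 5 lists it as an aim at 3 months, and section 7.1 compares CFQ at 3 months and gives the 3-month follow-up that purpose. Section 10 intends to estimate effect sizes and use them in sizing a larger trial. No section says how the between-arm effect is estimated.

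**Analysis population.** Under the secondary clinical outcomes, section 7.1 compares people who have used the intervention with those who have not, and explains intention to treat as "assuming those randomised to receive the intervention use it as intended".

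**Stratification.** For the randomisation, "we will stratify for gender within the randomisation".

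**The concern.** People enter Phase 2 because one CFQ measurement was high. Part of a high score is chance or short-term fluctuation, so the group's mean is expected to be lower when measured again, whatever treatment is given. If the selecting score is also the baseline, that fall appears in full as change in both arms. A plot of change by arm, each with its own 95% CI, can then show clear improvement in both arms when the intervention does nothing.

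A reader may also judge the comparison by whether the two intervals overlap, which is a poor substitute for the interval of the difference. The stake is practical: the effect-size estimate feeds the next sample size, and the protocol does not say that this estimate is the randomised difference.

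Two wordings add to the risk. Section 10 describes the baseline as a clinical assessment, which the schedule does not contain. The explanation of intention to treat mixes allocation with use, in a protocol that also plans adherence and dose-response summaries.

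**Working it through.** **1. The plan's own figure.** Phase 2 is sized by recruitment: "This is based on invitation letters being sent out to 4000 patients, 2000 of whom we hope will participate in the survey", then "200 of which may have Long COVID fatigue related symptoms, with 100 agreeing to participate in the intervention study". So 4000 × 0.50 = 2000, × 0.10 = 200, × 0.50 = 100, which reproduces the target. The design text confirms it: "100 participants providing informed consent will be allocated 1:1 into a two-arm wait-list randomised control trial (RCT"), so 50 per arm. The implied screen-positive rate is 200/2000 = 10%.

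**2. Model and assumptions.** Scores are taken as normal with SD 1 in the survey population, with correlation ρ between survey and follow-up, selection above a cut-off c on the survey score, no treatment effect and no dropout. The protocol gives no ρ; I use 0.5 to 0.8. I add a 30% screen-positive rate because section 7.1 says the share meeting the CFQ cut-off is not known.

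**3. Expected fall in each arm.** With selected proportion p, the mean above the cut is m = φ(c)/p, and the fall is (1 − ρ) × m.

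- p = 10%: c = 1.28, m = 1.755. Falls: 0.5 × 1.755 = 0.88; 0.3 × 1.755 = 0.53; 0.2 × 1.755 = 0.35.
- p = 30%: c = 0.52, m = 1.159. Falls: 0.58, 0.35 and 0.23.

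**4. Compared with the by-arm interval.** Within the selected group the survey variance is v = 1 + c·m − m², that is 0.169 at 10% and 0.264 at 30%. The variance of change is (1 − ρ)²v + (1 − ρ²). The half-width with 50 per arm is 1.96 × √(variance/50).

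| p | ρ | Expected fall (SD) | By-arm 95% half-width (SD) |
|---|---|---|---|
| 10% | 0.5 | 0.88 | 0.25 |
| 10% | 0.7 | 0.53 | 0.20 |
| 10% | 0.8 | 0.35 | 0.17 |
| 30% | 0.5 | 0.58 | 0.25 |
| 30% | 0.7 | 0.35 | 0.20 |
| 30% | 0.8 | 0.23 | 0.17 |

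In every row the fall exceeds the half-width, so an interval centred on the expected change excludes zero with no treatment effect. At p = 50% and ρ = 0.8 it no longer does (0.16 against 0.17).

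**5. The randomised contrast.** In 4000 simulated null trials (p = 10%, ρ = 0.5) the mean within-arm change was −0.876 SD. The between-arm difference in change was −0.001 SD (SE 0.177), and the baseline-adjusted difference was −0.001 SD (SE 0.173). The fall cancels between arms.

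**6. Overlap of two intervals.** With equal half-widths h, the difference has half-width √2 × h = 1.41h, but the two intervals overlap until the difference reaches 2h. At p = 10% and ρ = 0.5, h = 0.247, so an observed difference between 0.35 and 0.49 SD would have a CI excluding zero while the by-arm intervals overlap.

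**7. What baseline adjustment adds.** Per-person variances are 1 − ρ² (adjusted), (1 − ρ)²v + 1 − ρ² (change) and ρ²v + 1 − ρ² (3-month score alone).

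- Against change scores, the reduction runs from 1 − 0.360/0.367 = 2% (p = 10%, ρ = 0.8) to 1 − 0.750/0.816 = 8% (p = 30%, ρ = 0.5).
- Against the 3-month score alone, it runs from 1 − 0.750/0.792 = 5% (p = 10%, ρ = 0.5) to 1 − 0.360/0.529 = 32% (p = 30%, ρ = 0.8).

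**The case against.** A reader might infer that the protocol shows clinical effects only as within-arm change. It does not: sections 5, 7.1 and 10 plan a 3-month comparison, outcome values as well as changes, and effect-size estimates. Nor does regression to the mean bias the trial, since the control arm removes it in expectation (step 5). Both points stand and limit the finding to how the results are displayed and what is named as the effect.

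The choice of model and covariates is commonly left to a SAP, which is not shown here. That stands too: silence on adjustment is not an error, and the protocol nowhere rules it out. Adjustment is offered only as the better form of the estimate.

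The clinical measures are secondary and no formal testing is planned. This lowers the stakes but does not remove them, because effect estimates are to inform the next trial.

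The sizes rest on an assumed correlation and a normal model. The 10% is a Long COVID symptom rate at 4 weeks or longer, not a CFQ rate. They also apply to the CFQ alone: SF-12 and EQ-5D-5L did not select participants, and their shift was not calculated.

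A reader might also infer that the CFQ must be repeated before randomisation. The protocol reuses the survey on purpose to spare participants, and nothing in it shows that a repeat is needed.

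What the objection does not answer is the wording. The label on the baseline contradicts two other places, and intention to treat makes no assumption about use.

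**Conclusion.** The point holds in a limited form. The planned intervals for clinical measures do not include one for the between-arm difference. For the CFQ, by-arm change from the selecting score is expected to show a fall of about 0.35 to 0.88 population SD at a 10% screen-positive rate, or 0.23 to 0.58 SD at 30%, with no treatment effect. This assumes normal scores and correlations of 0.5 to 0.8. It distorts the reading of the by-arm display, not the randomised comparison. The two wording faults hold without any assumption. The gain in precision from adjustment is modest, because selection narrows the baseline range, and is not the main reason to act. This should be corrected before analysis, but it does not threaten the feasibility aims.

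**What to change.** In section 10, state that the clinical effect estimate is the between-arm difference at 3 months with its 95% CI, for CFQ and likewise for SF-12 and EQ-5D-5L. All randomised participants are analysed in their allocated arm irrespective of use, with a linear model adjusting for the Phase 1 score of that measure and gender. Say that this estimate is the one carried into planning the larger trial, and that within-arm changes are descriptive only.

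Also in section 10, describe the baseline as the Phase 1 survey. In section 7.1, replace the comparison by use, and the explanation of intention to treat, with analysis by allocated arm. Keep adherence and dose-response summaries separate.

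The cost is a few sentences and one regression per outcome. Survey score, gender and 3-month outcomes are already to be collected, so no visit, measure or participant is added.

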	Automatic screening for Phase 2 eligibility							-	-			t	-		Participant
Quantitative	Data analysis: Survey data					-				+		t	-	$\vdash$	MH/SB
Quantitation	Data linkage to eligible Phase 2 participants				_					-		t	-		SB
hase 2: Walt-list Inter		_	-		-	-			-	- 1	_		-		
and the second se	NLY offered to Phase 1 participants			-		1						i –	 	i i i	
	Participant receives Phase 2 PIS & CF online											1	-		QUALTRICS
	Participant provides contact details											í	-	E i	Participant
	Explain Phase 2 & consent by phone											í –	 	$\square$	RA/LR
Recruitment	Participant consents		6												RA/LR
	RDZ allocation														MH
Intervention phase	Particpant receives intervention immediately or in 3m		1	1	II	I									RA/LR
	Intervention phase (3m)												 		Participant & OM
Fup 3m	Data collection 3m using same online gsts	-													
	Wait-list group receive intervention					W	w	w	W				_		RA/LR
	Intervention phase (3m)											-	_		Participant & OM
Fup 6m	Data collection 6m using same online gsts					_						_	_		RA/LR
Qualitative intervie	Interviews with participants both arms				_	-						-	 		RA/LR
Quantitative	Interviews transcribed & analysed Data analysis: feasibility & intervention			$\rightarrow$		-		-				7	-		RA/LR/OM
utputs & Disseminatio		_	H	-	-	+-	-	-	_	-	_	1	-	-	MH/LR/AH/RP/RA/C
Outputs	Preparation Research paper / conference abstracts			$\rightarrow$		-	-	-			_	-	8		ALL
Outputs	Feedback to participants & GPs			$\rightarrow$		-	$\leftarrow$	-	-			-		9	ALL
	Preparation and submission larger funding bid			-		-								10	ALL
Final Reporting & retu	rn unspent funds to funder				-	-						1			LR/AH
anagement			1	_	-	1	-	-	_	-	_	+	_		
	ission / Annual & End of study reporting	PRE			1	1							-	11	LR/AH
PPIE Advisory Panel m		PRE	1										-		LR/OM
Fortnightly Research meetings Recruitment Review - decision to expand recruitment area		PRE	2												LR/AH/RP
					3							1	-		ALL

Prite Advisory Panel
Portnightly Research Steering Meetings
Recruitment Reviews
Promote study to GPs
First participant in Phase 1 Survey
First participant in Phase 2 RCT

8 Research Paper submitted 9 Participant feedback 10 Further funding bid 11 End of study reporting

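### The 3-month adherence sheet exists in one arm only and can unmask the statistician, and the dose-response estimate built on it rests on self-chosen use, an ambiguous zero-dose rule and an inconsistently described instrument

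*Protocol*

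**What the plan says.** **Dose rule.** Section 10 (Analysis) says adherence will be used to estimate dose response. Daily use of all three components as intended is the full dose: "this will be deemed full intervention, with non-use of any stages of the intervention as a zero dose". The same section will report "the proportion completing 50% and 100% intervention (using patient reported compliance sheet") in the flow chart.

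**Instrument.** Section 5 speaks of a tick sheet at follow-up. Section 7.1 (Randomisation) describes one additional tick sheet, "which will be sent to the intervention participants at 3m and 6m", and to the wait-list arm at 6 months only. Table 1 (Follow-ups) calls the item an intervention diary and marks it at 3 months as "intervention group only". Section 10 calls it a compliance sheet.

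**Masking.** Section 7.1 gives randomisation to an independent member of the biostatistics group, so that the statistician who does the analyses "remains masked to treatment allocation". Section 9 repeats that the statistician will be blind to group. In the work plan, the row "RDZ allocation" carries the initials of that same analysing statistician in the column for who is responsible.

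**Size.** "100 participants providing informed consent will be allocated 1:1 into a two-arm wait-list randomised control trial", so about 50 per arm.

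**The concern.** Assessing compliance is one of the stated aims, so the adherence measure is a deliverable of this feasibility study.

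- **Masking.** The planned dose-response analysis needs the 3-month sheets, and only one arm has them. The protocol nowhere says they are withheld, handled by someone else or released late.
- **Confounding.** Participants are selected for fatigue and offered a daily three-part routine. Those who are worse, or getting worse, may use it less. A relation between use and outcome is then not protected by randomisation. Section 10 attaches no caveat or adjustment to the term dose response. It also says that effect sizes from this study will help plan a larger trial, so a misleading slope could be carried forward.
- **Scoring.** The rule fixes only the two ends, and one end is ambiguous. Partial users are expected: the section on qualitative interviews plans to speak to people who used the technique to all or some extent.
- **Recording.** A definition that turns on daily use needs to know whether use is noted as it happens or recalled over about three months.

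**Working it through.** **1. Sample size.** Section 7.1 states the funnel from 4000 invitations: "2000 of whom we hope will participate in the survey, 200 of which may have Long COVID fatigue related symptoms, with 100 agreeing to participate". 4000 × 0.50 × 0.10 × 0.50 = 100, which reproduces the plan's figure; 100 / 2 = 50 per arm. No alpha, power, effect size or SD is stated. What follows is illustration under assumed inputs.

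**2. Two readings of zero dose.** Let q be the assumed probability that a participant does not use a given component, independently across the three. Expected zero-dose participants among 50:

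- any one component missed: 50 × [1 − (1 − q)³]
- no component used: 50 × q³
- non-use fully correlated across components: 50 × q on either reading

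| q (assumed) | One missed | None used | Fully correlated, both readings |
|---|---|---|---|
| 0.10 | 13.5 | 0.05 | 5 |
| 0.20 | 24.4 | 0.4 | 10 |
| 0.30 | 32.9 | 1.35 | 15 |

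The readings diverge as soon as some people use some components and not others, and coincide only if use is all or nothing.

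**3. A use-outcome slope with no intervention effect.** Assume n = 50 users, correlation 0.7 between severity and outcome, and correlation −a between severity and use. With no intervention effect:

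- *Final score, unadjusted.* Expected correlation of use with outcome is −0.7a: −0.21 for a = 0.3 and −0.35 for a = 0.5. In 4,000 simulated trials the 95% interval excludes zero in about 32% and 72%.
- *Change from baseline*, if baseline measures severity exactly and with equal variance. Correlation = (a − 0.7a) / √(2 − 1.4): 0.09 / 0.775 = +0.12 and 0.15 / 0.775 = +0.19. The sign reverses, and a slope favouring use with an interval excluding zero appears in under 1% of runs.
- *Baseline-adjusted*, severity measured exactly. Partial correlation 0; about 5% of intervals exclude zero, the nominal rate.
- *Baseline-adjusted*, baseline score correlating only 0.7 with severity. Partial correlation = (−0.7a + 0.7a × 0.49) / √[(1 − 0.49a²)(1 − 0.49²)], which is −0.13 and −0.22; about 14% and about one third of intervals exclude zero.

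The bias can therefore be absent, reversed or large. Section 10 mentions changes from baseline for the outcome plots by group but gives no model for the dose-response estimate.

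**4. Masking.** Every returned 3-month sheet belongs to the intervention arm. If a fraction r of that arm returns it (assumed), and everyone without a sheet is guessed to be wait-list, the proportion correctly placed is (50r + 50) / 100: 100% at r = 1.0, 90% at 0.8, 80% at 0.6. This applies only if the sheets, linked to participant ID, reach the statistician before the by-arm analysis.

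**5. Work plan against Section 7.1.** Section 7.1: allocation by an independent member, analysing statistician masked. Work plan: allocation row with the analysing statistician's initials. The table is badly extracted and some Phase 1 rows look displaced, but the rows next to this one match their tasks. The conflict is apparent rather than certain.

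**The case against.** The best defence has several parts.

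**It is an ancillary analysis.** Primary outcomes are recruitment and retention, formal testing of effectiveness is disclaimed, and outcomes are presented by randomised group. That stands and limits the consequence. It does not make a confounded slope a dose response.

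**The model may be in an analysis plan that is not shown.** That also stands for the model and its adjustment. The ambiguous rule, the differing names and the masking statements are in the protocol itself.

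**The plural suggests that zero dose means no component used.** This is a fair reading, and 50% completion then fits between the two ends. Partial use still has no score, and the other reading remains open.

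Some stronger readings are tempting but not supported:

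- A reader might infer that adherence is recalled only once. The intervention arm gets the sheet at both 3 and 6 months, and Table 1 calls it a diary. Recall once per three-month period is one possibility.
- A reader might infer that compliance will be overstated because only returners count. No returners-only denominator is stated, and Section 10 says missing data will be assessed.
- A reader might quote 32% or 72% as the plan's false-positive rate. Those figures need an unadjusted final-score model that the protocol does not specify.
- A reader might say masking is certainly lost. It depends on when the statistician receives the sheets, which the protocol leaves open. With descriptive summaries the practical effect may be modest.

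**Conclusion.** The concern holds on four limited points.

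- **Masking.** The masking statements are not secured by the data flow described. Each returned 3-month sheet identifies an intervention participant if it reaches the statistician before the by-arm analysis, and the work plan appears to contradict the independent randomisation.
- **Dose response.** The estimate rests on use chosen after randomisation and can arise with an inert intervention. Its size and even its direction depend on assumed correlations and on how baseline enters, so no percentage should be attributed to the plan.
- **Zero dose.** The phrase has two readings. At an assumed 20% independent non-use per component they give 24.4 and 0.4 of 50 participants; under full correlation they agree at 10.
- **Instrument.** Its three names leave open whether daily use is recorded or recalled.

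None of this touches the recruitment and retention outcomes. It does affect the compliance aim and the truth of the masking statement, and it should be corrected.

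**What to change.** 1. State that adherence data are withheld from the statistician until the 3-month by-arm analysis is locked. Reconcile the work-plan allocation row with Section 7.1.
2. For analysis, define zero dose as no component used. Score partial use on a graded scale, for example component-days done / (3 × days in the period). Report 50% and 100% completion with everyone allocated to the intervention as denominator, and show non-returners.
3. Call any use-outcome relation descriptive and baseline-adjusted, and drop the term dose response. If an effect of use is wanted, add an exploratory complier-average estimate at 3 months with randomised arm as instrument. State its definition of compliance and its exclusion restriction, which is doubtful in an unmasked wait-list trial with self-reported outcomes. Expect a wide interval.
4. Supply the sheet with the intervention pack so that use is recorded as it happens, in line with the diary in Table 1, and use one name for it throughout.

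Items 1 to 3 cost wording and a little analysis. Item 4 adds some recording burden for fatigued participants and may itself prompt use. Because adherence is a feasibility question here, that possibility should be acknowledged in the report.
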